#### 4.1.2 Characteristics of gut microbiota and serum metabolites in patients with DKD and their correlation with prognosis

(1) The fecal and blood samples were collected and analyzed by 16S rRNA sequencing, non-targeted metabolites and inflammatory factors.

(2) The biomarkers associated with poor prognosis were screened.

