#### 4.1.3. Gut Microbiota and Serum Metabolites in DKD Patients with Different Blood Glucose Variability Groups and Their Correlation with Prognosis

(1) Patients with DKD were divided into high GV group and low GV group according to GV status, and the intestinal microbiota characteristics and serum metabolites characteristics of patients in different GV groups were analyzed.

(2) Based on the association between gut microbiota, serum metabolic biomarkers and prognosis, the relationship between the bacterial co-abundance group (CAG) and the functional modules of serum metabolites was further established to explore their correlation with glycemic variability and poor prognosis.

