## 5.4 Methods for Determining the Required Sample Size for Research

This exploratory study investigates the impact of gut microbiota and related metabolites on prognosis in diabetic kidney disease (DKD) patients. To achieve this, patients will be divided into two groups based on adverse prognosis outcomes, with subsequent comparisons of gut microbiota and metabolite differences between groups. To minimize microbial variations caused by individual differences, each group requires at least 30 participants, meaning there must be at least 30 patients with adverse prognosis events. Drawing from existing research, a 2023 study published in *\*Diabetes Care\** [Diabetes Care.2023;46(4):868-873.] included 975 DKD patients with an average follow-up of 4.7 years, reporting 156 major outcomes of DKD progression. Consequently, the total sample size was calculated as  $975/156*30=187.5$ . Considering potential dropouts and incomplete responses, we typically increase the sample size by 10%, ultimately enrolling 210 patients as the modeling cohort. Additionally, 60 DKD patients were included as a validation cohort. During actual recruitment, sample size adjustments may be made based on factors such as recruitment speed and data quality. Regular assessments of sample adequacy should also be conducted to ensure statistical power.

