### 5.8.2 Statistical Analysis

Descriptive statistical analysis was performed on the collected data. Continuous variables were presented as mean  $\pm$  standard deviation (or median and interquartile range), while categorical variables were expressed as frequency and percentage. For intergroup comparisons of continuous variables, independent samples t-test or Mann-Whitney U-test was selected based on data normality. In cases involving multiple group comparisons, one-way ANOVA or Kruskal-Wallis test was employed. Categorical variable comparisons utilized chi-square test or Fisher's exact test to assess significant differences between groups. To evaluate relationships among multiple variables, linear regression was applied to continuous variables, logistic regression to categorical variables, and Cox proportional hazards regression to time-to-event data. These analyses adjusted for potential confounders such as age, sex, disease duration, and baseline glucose levels to ensure result accuracy and reliability. Confounding factors were included in regression analyses to minimize their impact. Additionally, propensity score matching was used to balance baseline characteristics between groups, ensuring comparability and enhancing the internal validity of the study results.

After adjusting for various covariates, we examined the association between adverse prognosis, hyperglycemic variability, and the gut microbiota  $\alpha$ -diversity index. The relationship between hyperglycemic variability, adverse prognosis, and  $\beta$ -diversity differences was tested using genus-level Bray-Curtis distance-based permutation ANOVA (PERMANOVA). Using MaAsLin, we identified gut microbiota communities potentially associated with adverse prognosis and hyperglycemic variability by comparing hyperglycemic variability groups with hypoglycemic variability groups, and prognostic favorable groups with unfavorable groups. OPLS-DA was employed to identify target metabolites potentially related to hyperglycemic variability and adverse prognosis, with adjustments made through linear regression. Mediation analysis was conducted to evaluate whether gut microbiota metabolism might mediate the association between hyperglycemic variability and adverse prognosis. Sensitivity analysis was performed to test the robustness of the mediation effect.

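### Target metabolites are selected by OPLS-DA, which uses the group label and no covariates; if error is then controlled only among those selected, the false-discovery rate can be several times nominal

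*Protocol*

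**What the plan says.** Section 5.8.2 names the selecting method and the adjusting method in one sentence: "OPLS-DA was employed to identify target metabolites potentially related to hyperglycemic variability and adverse prognosis, with adjustments made through linear regression". It applies to two contrasts, glycemic variability (GV) and prognosis. Earlier in the same section, the covariates of the regression analyses are given: "These analyses adjusted for potential confounders such as age, sex, disease duration, and baseline glucose levels to ensure result accuracy and reliability".

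Section 4.1.2 makes the screening of prognostic biomarkers part of the research content: "The biomarkers associated with poor prognosis were screened". Section 3.1 lists such screening among the specific objectives under the main objective.

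No data split is described for the metabolite list. Section 5.4 adds separate patients ("Additionally, 60 DKD patients were included as a validation cohort"), but sections 4.1.4 and 5.8.2 use them to validate the prediction model, not to confirm individual metabolites.

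The protocol gives no VIP cut-off, significance level, multiplicity procedure or number of metabolites. Those details may sit in a statistical analysis plan and their absence is not the point here. The point is the stated choice of OPLS-DA as the selector.

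**The concern.** OPLS-DA looks for the direction in the metabolite data that best separates the labelled groups. A metabolite ranks high because it differs between those groups in those patients. A regression p-value for the same label in the same patients is then not a fresh test: null metabolites that survive the filter have p-values pushed towards zero. A multiplicity correction that counts only the survivors treats those p-values as if they were uniform between 0 and 1.

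There is a second, separate problem. The filter takes no covariates. A metabolite whose association appears only after adjustment for, say, disease duration can be lost before the adjusted model is fitted.

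At stake is the list of prognostic and GV-related metabolites, which is a main product of the study.

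**Working it through.** **The plan's own figure.** Section 5.4 requires 30 events ("each group requires at least 30 participants, meaning there must be at least 30 patients with adverse prognosis events") and takes its event rate from a published cohort that "included 975 DKD patients with an average follow-up of 4.7 years, reporting 156 major outcomes of DKD progression". 156/975 = 16.0%, and 30/0.16 = 187.5, as stated. Adding 10% gives 187.5 × 1.10 = 206.3; dividing by 0.9 gives 208.3, so 209. Both are close to the 210 enrolled, so the figure is reproduced.

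**Inputs from the protocol.** The modelling cohort is 210. For prognosis, 210 × 0.9 = 189 patients with the planned 30 events gives 30 against 159. For GV, section 4.1.3 has two groups ("Patients with DKD were divided into high GV group and low GV group according to GV status"); an even split, 105 against 105, is assumed.

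**Assumptions not in the protocol.** 300 to 1,000 metabolites; 0 to 30% truly different, by 0.6 SD; VIP cut-off 0.8 to 2; Benjamini-Hochberg (BH) at 5%.

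**Step 1, no true signals.** With one predictive component the weight is proportional to X'y, and the mean squared VIP is 1. VIP>1 then means |Z|>1, and P(|Z|>1) = 0.317. Among the survivors 0.05/0.317 = 15.8% have p<0.05, and BH counted over survivors is inflated by 1/0.317 = 3.15.

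**Step 2, some true signals.** VIP>1 now means |Z| above its root mean square, c = √(1 + π·δ²). Here π is the share of true signals and δ = 0.6/√(1/n₁ + 1/n₂), which is 4.35 for GV and 3.01 for prognosis. With q = P(|Z|>c), the FDR of BH within the selected set is about 0.05 × (null share of the selected set)/q, as long as BH does not simply reject everything selected. At π = 10%:
- GV: c = 1.70, q = 0.089. Selected: 0.9 × 0.089 + 0.1 × 0.996 = 0.180. Null share 0.080/0.180 = 0.446. FDR ≈ 0.05 × 0.446/0.089 = 0.25.
- Prognosis: c = 1.38, q = 0.167. Selected: 0.9 × 0.167 + 0.1 × 0.949 = 0.245. Null share 0.150/0.245 = 0.613. FDR ≈ 0.05 × 0.613/0.167 = 0.18.

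**Step 3, simulation** (300 replicates per setting, covariate-adjusted regression, BH 5%). The ratio is the FDR within the selected set divided by the FDR over all metabolites.

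| Setting | FDR, all | FDR, selected set | Ratio |
|---|---|---|---|
| VIP>1, no signals | 0.05–0.07 | 0.15–0.18 | 2.5–3.1 |
| VIP>1, 5–10% signals | 0.04–0.05 | 0.18–0.24 | 3.6–5.5 |
| VIP>1, 10%, correlation 0.5 | 0.04–0.05 | 0.17–0.24 | 4.0–4.9 |
| VIP>1, 10%, confounding | 0.04–0.05 | 0.16–0.21 | 3.6–4.5 |
| VIP>1, 30%, GV | 0.04 | 0.03 | 0.9 |
| VIP>1, 30%, prognosis | 0.03–0.04 | 0.11 | 3.2–3.3 |
| VIP>0.8, 10% | 0.04–0.05 | 0.13–0.17 | 2.7–3.8 |
| VIP>1.5, 10% | 0.04–0.05 | 0.11–0.30 | 2.5–6.5 |
| VIP>2, 10% | 0.04–0.05 | 0.01–0.08 | 0.2–1.8 |

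The 0.07 in the first row is one all-null run and is put down to Monte Carlo error. The ratio falls below 1 when the filter is so strict that it removes nearly all null metabolites by itself.

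**Step 4, raw p<0.05.** FDR = (1−π) × 0.05 / [(1−π) × 0.05 + π × power], with power 0.99 (GV) and 0.85 (prognosis).
- π = 5%: 0.0475/(0.0475 + 0.0496) = 0.49 and 0.0475/(0.0475 + 0.0427) = 0.53.
- π = 10%: 0.045/(0.045 + 0.099) = 0.31 and 0.045/(0.045 + 0.085) = 0.35.

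In simulation with VIP>1 these values are the same with and without the filter. A separate simulation (500 metabolites, 5% signals, VIP>1) gave 0.47–0.61 for this route, 0.15–0.23 for BH within the selected set, and about 0.05 when all metabolites were tested with adjustment.

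**Step 5, order of steps.** Adjusting first and running OPLS-DA on the residuals still gives a ratio of 5.0–5.2 (GV, VIP>1, BH within the selected set). The inflation comes from selecting and testing on one label, not from the missing covariates.

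**Step 6, lost markers.** In the separate simulation, under assumed confounding in the 105/105 contrast, the unadjusted filter cut the detection of true markers from 0.65 to 0.41.

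**The case against.** The strongest reply is that the inflation needs a procedure the protocol does not write down: a VIP cut-off, a BH step, and a correction counted only over survivors. That is correct. A reader might infer that the plan triples the FDR. The documents do not support this as a fact: 3.15 is the all-null case under one cut-off and one correction rule, and the ratio ranges from 0.2 to 6.5 over the settings tried.

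A reader might also infer that the filter always adds false markers. It does not. With raw p<0.05 and VIP>1 under the null, 31.7% × 15.8% = 5.0% of all metabolites pass both steps, the same as without a filter. This does not rescue the plan, because an uncorrected list is poor for another reason (Step 4).

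Two further inferences go beyond the text. Section 5.8.2 applies MaAsLin to the microbiota but states no covariates or error control for that step, so the plan cannot be said to treat genera correctly and metabolites wrongly. Nor does it say that the OPLS-DA list feeds the mediation analysis, though that is plausible.

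It also stands that the order of steps is ambiguous, that section 5.4 calls the study exploratory, and that the prediction model has its own feature selection and validation. These points limit the consequences. They do not remove the objection to the stated selector, since the metabolite list is itself an objective and no separate patients are set aside to confirm it.

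**Conclusion.** The point holds in conditional form. Section 5.8.2 gives the identification of target metabolites to a supervised method without covariates, on the natural reading in the same patients as the adjusting regression. The two obvious continuations both leave the list poorly controlled:
- Correction within the selected set: FDR about 3 to 5 times nominal under VIP>1, BH 5% and 0 to 10% true signals. With 30% signals in the GV contrast, or with VIP>2 in the GV contrast, there is no inflation.
- No correction: FDR about 0.3 to 0.6 with 5 to 10% true signals, with or without the filter.

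The loss of confounder-masked markers is a real possibility, but its size rests wholly on the assumed confounding. For an exploratory study this should be changed before analysis; it does not invalidate the design.

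**What to change.** In section 5.8.2, replace the OPLS-DA sentence with the following plan. Fit the covariate-adjusted regression to every measured metabolite, for the GV contrast and for the prognosis contrast. Control the FDR over the full set of metabolites and take the target list from that result. In the simulations this kept the FDR at about 0.03 to 0.05, apart from the one all-null run at 0.07.

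Keep OPLS-DA as a descriptive display with permutation-tested Q2. The permutation test matters because, on pure noise with 210 patients and 1,000 features, the apparent AUROC of the predictive component was 0.94 to 1.00. Alternatively, require the VIP criterion in addition to full-set FDR control; that never raised the FDR above the full-set value.

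The change needs no new patients, assays or software. The downside is a shorter metabolite list.

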**Principal Investigator: [name]**

**date :** **YTD**

## **I. Summary of the Research Plan**

Diabetic kidney disease (DKD), one of the most significant microvascular complications of diabetes, has become the leading cause of end-stage renal disease. Glycemic variability (GV) is considered closely associated with disease progression in these patients. Recent studies indicate that gut microbiota and their serum metabolites play crucial roles in regulating glycemic variability and disease prognosis. However, the mechanisms by which gut microbiota and their metabolites influence glycemic variability and subsequently affect disease outcomes in DKD patients remain unclear. This study aims to address three key questions: ① Characterizing gut microbiota and serum metabolites in DKD patients with varying disease stages and progression levels, while precisely evaluating the prognostic value of gut microbial markers for adverse outcomes. ② Investigating the relationship between gut microbiota, serum metabolites, and glycemic variability in DKD patients. ③ Determining whether gut microbiota and serum metabolites interfere with glycemic variability to influence disease prognosis. To address these questions, this observational prospective cohort study will enroll 270 patients with diabetic kidney disease. By integrating continuous glucose monitoring (CGM), 16S rRNA high-throughput sequencing, and serum non-targeted liquid chromatography-mass spectrometry (LC-MS), this study evaluated glycemic variability, analyzed gut microbiota and serum metabolites, and constructed and validated predictive models for poor prognosis in diabetic kidney disease (DKD) patients. The findings revealed correlations between gut microbiota, serum metabolites, and glycemic variability, elucidated their prognostic roles in DKD, and provided early identification tools for high-risk DKD patients. We aim to offer novel perspectives and strategies for DKD prognosis management, thereby improving clinical outcomes and quality of life for patients.

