#### **2.1.4 Hypothesis and Significance of the Research**

To date, no studies have explored the impact of gut microbiota on the prognosis of diabetic kidney disease (DKD) patients with varying degrees of glycemic variability. Based on existing literature, we propose the following hypotheses: 1) Glycemic variability and specific gut microbiota serum metabolites serve as predictors of adverse cardiovascular events in DKD patients; 2) The gut microbiota and serum metabolites of DKD patients are associated with glycemic variability (GV), which may influence patient outcomes through gut microbiota metabolism. Our proposed methodology includes: 1) Assessing glycemic variability in DKD patients via continuous glucose monitoring (CGM) to investigate its relationship with prognosis and determine optimal glycemic variability control targets. 2) Utilizing 16S rRNA high-throughput sequencing and serum non-targeted liquid chromatography-mass spectrometry (LC-MS) to analyze the relationship between gut microbiota, metabolites, inflammatory factors, and DKD patient prognosis. This study aims to optimize clinical management strategies, establish risk prediction models, promote interdisciplinary research, and improve patient quality of life. The findings will provide new scientific evidence and tools for precision treatment and prognosis management in DKD patients, demonstrating significant scientific and clinical value.

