### (2) Wear a Continuous Glucose Monitor and Collect Samples

All enrolled subjects were required to wear a continuous glucose monitor (CGM) for 14 days during their first 24-hour hospital stay. Endocrinologists provided personalized dietary guidance based on blood glucose levels, with standardized glucose-lowering regimens. Significant deviations from baseline glucose levels warranted necessary dosage adjustments. Blood glucose variability metrics were collected after 14 days. Additionally, stool and blood samples from all participants were collected and preserved for subsequent analysis.

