#### **5.6 Experimental Scheme**

Step	Period	Filter period	Period of wearing CGM			Follow-up period		
	Study follow-up	Visit 0	Visit 1	Visit 2	Visit 3	Visit 4	Visit 5	Visit 6
	Study date (days)	1 day before enrollment	1 day after enrollment	7 days after enrollment	14 days after enrollment	Within 1 year after enrollment	Within 2 years after enrollment	Within 3 years after enrollment

1	Selection and exclusion criteria	✓						
2	Sign the informed consent form.	✓						
3	Adorn CGM		✓					
4 clinical data	Basic information of the subjects		✓					
	Clinical diagnosis		✓					
	Personal history		✓					
	History of past illness		✓					
	Check-up		✓					
5 clinical examination Inspection	Routine blood test			✓				
	Liver function			✓				
	Renal function			✓				
	HbA1c			✓				
	Blood fat			✓				
	Fasting insulin (FIns)			✓				
	Blood sugar			✓				
	Thyroid function			✓				
	Coagulation function			✓				
6	Medication during CGM monitoring				✓			
7	Fecal collection		✓					
8	Blood collection		✓					
9	Medications taken after discharge				✓			

10	Download the CGM report				✓			
11	Fecal microbiota sequencing					✓		
12	Metabolite assay in serum					✓		
13	Progression events of DKD during follow-up					✓	✓	✓
14	Assessment of MACE events during follow-up					✓	✓	✓
15	Death events during follow-up		✓	✓	✓	✓	✓	✓
16	Adverse event monitoring		✓	✓	✓			
17	Deviation from plan record		✓	✓	✓	✓	✓	✓
18	Fill in CRF		✓	✓	✓	✓	✓	✓

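### Key question 3 makes glycemic variability (GV) the mediator between gut and prognosis, but the only planned mediation analysis makes gut metabolism the mediator between GV and prognosis

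*Protocol*

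**What the plan says.** The Protocol describes the gut–GV–prognosis pathway in four places.

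- **Section I, knowledge gap:** "the mechanisms by which gut microbiota and their metabolites influence glycemic variability and subsequently affect disease outcomes in DKD patients remain unclear". The order is gut, then GV, then outcome.
- **Section I, key question 3:** "Determining whether gut microbiota and serum metabolites interfere with glycemic variability to influence disease prognosis". GV is again the step through which the gut acts.
- **Section 2.1.4, hypothesis 2:** "The gut microbiota and serum metabolites of DKD patients are associated with glycemic variability (GV), which may influence patient outcomes through gut microbiota metabolism". Here GV comes first and gut metabolism is the route to outcome.
- **Section 5.8.2:** "Mediation analysis was conducted to evaluate whether gut microbiota metabolism might mediate the association between hyperglycemic variability and adverse prognosis". Exposure is high GV, mediator is gut metabolism, outcome is adverse prognosis. (The section contrasts high and low GV groups, so its term for the exposure is read here as high GV.)

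The objectives in sections 3.1 to 3.2.2 ask for relationships, prediction and correlations, and fix no causal order. Section 4.1.3 and the 2028 association analysis in section 9 rely on correlation and regression. No other mediation analysis is described.

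**The concern.** Exposure and mediator are swapped between the question and the analysis. An indirect effect belongs to one stated order of variables: the effect of GV that passes through the gut is a different quantity from the effect of the gut that passes through GV. Followed as written, the study reports the first, while key question 3 asks for the second.

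The practical risk is a misread null. If the gut affects prognosis by way of GV, the planned analysis should find little or no indirect effect, and the report could say that no mediation was found although the path named in question 3 was present. If the mismatch is noticed only once outcomes are known, the choice of direction becomes post hoc.

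**Working it through.** The protocol gives no figure for mediation, so there is none to reproduce. The check sets the texts side by side and then works through the algebra.

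**Step 1. Roles of the variables**

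| Place in Protocol | Exposure | Mediator | Outcome |
|---|---|---|---|
| Section I, knowledge gap | gut/metabolites | GV | disease outcomes |
| Section I, key question 3 | gut/metabolites | GV | prognosis |
| Section 2.1.4, hypothesis 2 | GV | gut metabolism | patient outcomes |
| Section 5.8.2, mediation | GV | gut metabolism | adverse prognosis |

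The first two rows agree with each other, as do the last two. The pairs are opposite.

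**Step 2. What each model estimates**

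Let G be a gut or metabolite measure, V be GV and Y the outcome. Both models use the same outcome regression, with linear predictor β_V·V + β_G·G.

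- Planned indirect effect = (slope of G on V) × β_G.
- Question 3 indirect effect = (slope of V on G) × β_V.

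**Step 3. Suppose question 3 is right**

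Let G affect V with path a, let V affect Y with path b, and let G have no other route to Y. Given V, G then carries no further information about Y, so β_G = 0 and β_V = b. With standardised variables the slope is a in either direction.

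- Planned: a × 0 = 0.
- Question 3: a × b.

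The path values below are assumptions; the protocol gives none. The fitted columns come from a linear model on 200,000 simulated patients and only confirm the algebra.

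| a | b | Question 3, a × b | Question 3, fitted | Planned, fitted |
|---|---|---|---|---|
| 0.3 | 0.3 | 0.09 | 0.091 | −0.001 |
| 0.3 | 0.5 | 0.15 | 0.152 | 0.000 |
| 0.5 | 0.3 | 0.15 | 0.150 | −0.001 |
| 0.5 | 0.5 | 0.25 | 0.250 | 0.000 |

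**Step 4. Can either model show direction?**

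No. Take two structures: (i) gut affects GV, which affects outcome; (ii) GV affects both gut and outcome, and the gut is inert. In both, G and V are correlated and Y depends on V alone, so they can give the same joint distribution. A question 3 model would report mediation in both, wrongly in (ii). By the same argument, the planned model would report mediation if the gut drove both GV and outcome while GV was inert.

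**The case against.** The strongest reply is that little information is missing. The planned outcome regression already contains GV adjusted for the gut measure, which is the coefficient question 3 needs, and the gut–GV association is estimated anyway. That is correct. A reader might infer that question 3 cannot be answered from this study; the documents do not support that. What is missing is the matching indirect effect and its interpretation.

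Second, hypothesis 2 and section 5.8.2 agree, and the outlier is a summary in translated English whose verb in question 3 could mean effect modification. Read alone, question 3 is loose. The knowledge-gap sentence, however, fixes the order as gut, GV, outcome, and section 5.8.2 names no interaction analysis of gut and GV either.

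Third, a statistical analysis plan that is not shown could add a second model. It could, but the protocol's own texts would still conflict.

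Three stronger readings are tempting and do not hold:

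- **That sampling order proves the planned direction wrong.** The schedule in section 5.6 ticks "Fecal collection" and "Blood collection" at Visit 1, one day after enrollment, whereas section 5.5 (2) says "Blood glucose variability metrics were collected after 14 days". But 14 days of monitoring may stand in for a patient's usual GV, particularly as inclusion requires an unchanged antidiabetic regimen for at least 3 months. The date of recording is not causal order, and the visit days are read from ticks in an extracted table.
- **That the sensitivity analysis is deficient.** Section 5.8.2 says "Sensitivity analysis was performed to test the robustness of the mediation effect". Its content is detail that a protocol may leave to the statistical analysis plan.
- **That mediation is underpowered.** The target of 30 events in section 5.4 serves a comparison of prognosis groups. The protocol makes no power claim for mediation, so there is none to correct.

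**Conclusion.** The point holds as a contradiction within the protocol. The knowledge gap and key question 3 make GV the mediator; hypothesis 2 and the only planned mediation analysis make gut metabolism the mediator. One of three key questions therefore has no matching indirect effect. If the path in question 3 is true, the planned indirect effect is expected to be about zero, against a × b for the effect asked about.

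The zero assumes that the gut reaches the outcome only through GV, that GV enters the regression in full and without appreciable measurement error, and that there is no uncontrolled confounding. If GV is reduced to high and low groups, some of its effect could remain attached to the gut measure, so about zero is the safer wording. The figures 0.09 to 0.25 illustrate assumed paths and are not forecasts.

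A null planned result would be a correct answer to the question in section 5.8.2; the error would lie in offering it as the answer to key question 3. Nor do the documents show which direction is biologically right. The study is called exploratory in section 5.4 and section 5.8.2 speaks of possible mediation, but section I promises a determination, so the limit on interpretation needs stating. The primary endpoint is not affected. This should be corrected before outcome analysis, but it is not a fundamental flaw.

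**What to change.** Before the outcome analysis that section 9 places in 2028:

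1. Reconcile section I, section 2.1.4 and section 5.8.2, and state which path answers which question.
2. Add to section 5.8.2 a second mediation model with the gut or metabolite measure as exposure, GV as mediator, and the same adverse-prognosis outcome and covariates as the planned model.
3. If the second model is not wanted, reword the knowledge gap and key question 3 in section I to match hypothesis 2 and section 5.8.2.
4. In either case, state that mediation results are exploratory and support no directional or causal claim, because gut and GV are measured almost simultaneously at baseline and neither model can establish direction.

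No new data are needed: the samples, the glucose monitoring and the follow-up are already scheduled, and the second model uses largely the same regression. The cost is one extra analysis and a more cautious conclusion, or under option 3 a change of wording and the same caution.

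### With stool and research blood taken once, at CGM fitting, the schedule does not establish that glycemic variability precedes the metabolite profile, so the mediation analysis in 5.8.2 cannot support a directional indirect effect of GV

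*Protocol*

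**What the plan says.** **The planned analysis.** Protocol section 5.8.2: "Mediation analysis was conducted to evaluate whether gut microbiota metabolism might mediate the association between hyperglycemic variability and adverse prognosis". I read the exposure as high as opposed to low GV, in line with the grouping in section 4.1.3. A sensitivity analysis of the mediation effect is announced but not described.

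**The sampling times.** In the schedule of section 5.6, the rows "Fecal collection" and "Blood collection" each carry one tick, at Visit 1 (one day after enrollment). The CGM is put on at that same visit. The row "Download the CGM report" is ticked at Visit 3 (14 days after enrollment). Section 5.5(2) agrees: "Blood glucose variability metrics were collected after 14 days". On samples that section says only: "Additionally, stool and blood samples from all participants were collected and preserved for subsequent analysis". It names no day, so the schedule is what fixes it.

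**Management during CGM wear.** Section 5.5(2): "Endocrinologists provided personalized dietary guidance based on blood glucose levels, with standardized glucose-lowering regimens". It adds that dosage may be adjusted when glucose departs significantly from baseline.

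**The direction of the pathway.** Hypothesis 2 in section 2.1.4 can be read as 5.8.2 is: GV acts on outcome through gut metabolism. The third key question in the Summary (section I) puts it the other way round: gut microbiota and serum metabolites act on GV, and through it on prognosis.

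**The concern.** An indirect effect of GV through gut metabolism is a statement about sequence: GV changes the metabolite profile, and the profile then changes prognosis. To carry that reading, the exposure should be known to come before the mediator. Here the mediator is sampled once, as the recording of the exposure begins, and there is neither a later research sample nor an earlier CGM recording.

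At stake is how a positive result would be read. A GV-metabolite correlation together with a metabolite-prognosis association would yield a non-zero indirect effect, and it could be reported as the mechanism by which GV harms the kidney. The same data would arise if gut state shaped GV, which is what the Summary proposes. The protocol thus offers two opposite pathways and a schedule that does not support the one chosen for analysis.

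**Working it through.** **1. Time line, from sections 5.6, 5.5(2) and 5.5(3)**

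| Element | Role in 5.8.2 | When |
|---|---|---|
| Stool and research blood | Mediator | Visit 1, day 1, once |
| CGM fitted | Exposure recording starts | Visit 1, day 1 |
| Dietary guidance, possible dosage adjustment | May alter the exposure | During CGM wear |
| CGM report, GV metrics | Exposure complete | Visit 3, day 14 |
| DKD progression, MACE, death | Outcome | Visits 4 to 6, within 3 years; deaths recorded from Visit 1 |

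Day 14 - day 1 = 13 days from the mediator sample to completion of the exposure recording. This applies to the modeling and validation cohorts alike: 210 + 60 = 270 patients. The 13 days are calendar spacing, not a measure of bias.

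**2. Is there another sample that could serve as a later mediator?** The row "Fecal microbiota sequencing" and the serum metabolite assay are ticked at Visit 4, but these are laboratory steps on stored material; no collection row is ticked there. The Visit 2 ticks are routine clinical tests. So there is none.

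**3. Each leg of the pathway**

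- GV to metabolites: order not established. Sampling and sensor fitting share Visit 1, and their order within the visit is not given. The accurate description is that samples are taken at the start of the CGM window.
- Metabolites to prognosis: order secured, since outcomes accrue after Visit 1.
- Reverse path (gut to GV to prognosis): the measurements fall in that order.

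**4. Can the fitted model tell the two directions apart?** An illustration with assumed values, none from the protocol:

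- Gut state M is standard normal.
- GV is r x M plus noise, scaled to unit variance.
- Outcome Y is b x M plus unit-variance noise.
- GV has no effect on M or on Y.

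The analysis in the 5.8.2 direction regresses M on GV (slope a), then Y on M and GV (slope b), and takes a x b as the indirect effect. Its expected value is r x b, for example 0.2 x 0.3 = 0.06 (simulated mean 0.0599). With n = 210, 2000 replicates and both slopes required to be significant, the share of studies finding an indirect effect of GV is:

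| r | b = 0.2 | b = 0.3 |
|---|---|---|
| 0.0 | 3.6% | 5.5% |
| 0.1 | 24.9% | 28.4% |
| 0.2 | 65.2% | 81.5% |
| 0.3 | 77.4% | 97.2% |

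A significant result therefore does not show that GV acts on gut metabolism. The model contains no sampling day, so the table illustrates that direction is not identified from such associations in general. It does not measure the effect of the Visit 1 timing. Direction has to come from the design or from a stated assumption, and neither supports GV first here.

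**The case against.** The strongest defence is that the date of measurement is not the date of the cause. GV does not begin when the sensor is fitted; 14 days of CGM can stand in for the patient's habitual GV. The inclusion criteria in 5.3.2 require at least 3 months on an unchanged antidiabetic regimen, so samples and CGM may both describe one baseline state ahead of 3 years of follow-up.

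Much of this stands. A reader might infer that the time order contradicts the mechanism; the documents do not support that. If GV is a stable trait, it may have preceded the Visit 1 sample, so the order is unestablished rather than reversed. A reader might also infer that the entire indirect effect lacks time order. That is too strong as well, because the metabolite-to-outcome leg is correctly ordered.

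The defence does not rescue the directional claim. The protocol nowhere states the stable-trait assumption, and the guidance and possible adjustments during wear weaken it by an amount the documents do not let one estimate: they do not say how many patients change treatment or how far GV shifts. Even if the assumption holds, GV and gut state become two measurements of one baseline, which still does not put GV first.

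The study also calls itself exploratory (5.4) and says only that metabolism might mediate an association. The decomposition can be computed; the directional reading is what lacks support. The unspecified sensitivity analysis may be set out in an SAP not at hand, but no analysis can supply a sample that was not scheduled.

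**Conclusion.** The point holds in a limited form. As scheduled, the study cannot establish that GV precedes the metabolite profile, so the mediation analysis in 5.8.2 cannot support an indirect effect running from GV through gut metabolism. One of the two legs is affected, in all 270 patients. The size of any bias cannot be derived from the documents. The protocol also states opposite pathways in the Summary and in 5.8.2, and the schedule fits the Summary better.

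This rests on reading the 5.6 schedule as the only source of sampling days, which nothing in the protocol contradicts, and on taking 5.8.2 at its word about which variable is exposure and which is mediator. The primary endpoint, the sample size and the prediction model are not affected. It is a matter of what may be concluded, and worth correcting because the correction is nearly free.

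**What to change.** Keep the Visit 1 samples and amend the text in one of two ways.

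1. **Association only.** In 5.8.2, state that the joint analysis of GV, metabolites and prognosis is reported as a baseline association, with no indirect effect or proportion mediated claimed for GV. Bring hypothesis 2 in section 2.1.4 into line.
2. **Reverse the pathway.** In 5.8.2, make gut features the exposure and GV the mediator, as in the Summary, and state that direction consistently in section I, section 2.1.4 and 5.8.2. The order of sampling within Visit 1 should then be stated. Freedom from confounding, for instance by diet or kidney function, remains an assumption to be declared.

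Either way the cost is a weaker mechanistic claim for hypothesis 2, plus a text amendment reported to the ethics committee under section 6.1. No procedure or sample-size figure changes, and section 9 places the association analysis in 2028.

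Moving collection to Visit 3 may seem the obvious remedy, but I do not recommend it. Those samples would follow 14 days of dietary guidance, although they also serve the biomarker objective in 3.1 and the prediction model built on baseline data. The move would also lose the order needed for the Summary's pathway, and by the table in the working it would not by itself identify direction.
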